11.1 Regulatory and ethical compliance

This clinical study was designed, shall be implemented and reported in accordance with the ICH Harmonized Tripartite Guidelines for Good Clinical Practice, with applicable local regulations (including European Directive 2001/20/EC and US Code of Federal Regulations Title 21), and with the ethical principles laid down in the Declaration of Helsinki.

11.2 Responsibilities of the investigator and IRB/IEC/REB

The protocol and the proposed informed consent form must be reviewed and approved by a properly constituted Institutional Review Board/Independent Ethics Committee/Research Ethics Board (IRB/IEC/REB) before study start. Prior to study start, the investigator is required to sign a protocol signature page confirming his/her agreement to conduct the study in accordance with these documents and all of the instructions and procedures found in this protocol and to give access to all relevant data and records to Novartis monitors, auditors, Novartis Clinical Quality Assurance representatives, designated agents of Novartis, IRBs/IECs/REBs and regulatory authorities as required.

11.3 Informed consent procedures

Eligible patients may only be included in the study after providing written (witnessed, where required by law or regulation), IRB/IEC/REB-approved informed consent, or, if incapable of doing so, after such consent has been provided by a legally acceptable representative of the patient. In cases where the patient's representative gives consent, the patient should be informed about the study to the extent possible given his/her understanding. If the patient is capable of doing so, he/she should indicate assent by personally signing and dating the written informed consent document or a separate assent form.

For Japan only, written consent is necessary both from the patient and his/her legal representative if he/she is under the age of 20 years.

Informed consent must be obtained before conducting any study-specific procedures (i.e. all of the procedures described in the protocol). The process of obtaining informed consent should be

documented in the patient source documents. The date when a subject's Informed Consent was actually obtained will be captured in their CRFs.

Novartis will provide to investigators, in a separate document, a proposed informed consent form (ICF) that is considered appropriate for this study and complies with the ICH GCP guideline and regulatory requirements. Any changes to this ICF suggested by the investigator must be agreed to by Novartis before submission to the IRB/IEC/REB, and a copy of the approved version must be provided to the Novartis monitor after IRB/IEC/REB approval.

Women of child bearing potential should be informed that taking the study medication may involve unknown risks to the fetus if pregnancy were to occur during the study and agree that in order to participate in the study they must adhere to the contraception requirement for the duration of the study. If there is any question that the patient will not reliably comply, they should not be entered in the study.

11.4 Discontinuation of the study

Novartis reserves the right to discontinue this study under the conditions specified in the clinical study agreement. Specific conditions for terminating the study are outlined in [Section 4.4](#).

11.5 Publication of study protocol and results

Novartis is committed to following high ethical standards for reporting study results for its innovative medicine, including the timely communication and publication of clinical trial results, whatever their outcome. Novartis assures that the key design elements of this protocol will be posted in a publicly accessible database such as www.clinicaltrials.gov before study start. In addition, results of interventional clinical trials in adult patients are posted on www.novartisclinicaltrials.com, a publicly accessible database of clinical study results within 1 year of study completion (i.e., LPLV), those for interventional clinical trials involving pediatric patients within 6 months of study completion.

Novartis follows the ICMJE authorship guidelines (www.icmje.org) and other specific guidelines of the journal or congress to which the publication will be submitted

Authors will not receive remuneration for their writing of a publication, either directly from Novartis or through the professional medical writing agency. Author(s) may be requested to present poster or oral presentation at scientific congress; however, there will be no honorarium provided for such presentations.

As part of its commitment to full transparency in publications, Novartis supports the full disclosure of all funding sources for the study and publications, as well as any actual and potential conflicts of interest of financial and non-financial nature by all authors, including medical writing/editorial support, if applicable.

For the Novartis Guidelines for the Publication of Results from Novartis-sponsored Research, please refer to www.novartis.com.

11.6 Study documentation, record keeping and retention of documents

Each participating site will maintain appropriate medical and research records for this trial, in compliance with Section 4.9 of the ICH E6 GCP, and regulatory and institutional requirements for the protection of confidentiality of subjects. As part of participating in a Novartis-sponsored study, each site will permit authorized representatives of the sponsor(s) and regulatory agencies to examine (and when required by applicable law, to copy) clinical records for the purposes of quality assurance reviews, audits and evaluation of the study safety and progress.

Source data are all information, original records of clinical findings, observations, or other activities in a clinical trial necessary for the reconstruction and evaluation of the trial. Examples of these original documents and data records include, but are not limited to, hospital records, clinical and office charts, laboratory notes, memoranda, subjects' diaries or evaluation checklists, pharmacy dispensing records, recorded data from automated instruments, copies or transcriptions certified after verification as being accurate and complete, microfiches, photographic negatives, microfilm or magnetic media, x-rays, and subject files and records kept at the pharmacy, at the laboratories, and medico-technical departments involved in the clinical trial.

Data collection is the responsibility of the clinical trial staff at the site under the supervision of the site Principal Investigator. The study case report form (CRF) is the primary data collection instrument for the study. The investigator should ensure the accuracy, completeness, legibility, and timeliness of the data reported in the CRFs and all other required reports. Data reported on the CRF, that are derived from source documents, should be consistent with the source documents or the discrepancies should be explained. All data requested on the CRF must be recorded. Any missing data must be explained. Any change or correction to a paper CRF should be dated, initialed, and explained (if necessary) and should not obscure the original entry. For eCRFs an audit trail will be maintained by the system. The investigator should retain records of the changes and corrections to paper CRFs.

The investigator/institution should maintain the trial documents as specified in Essential Documents for the Conduct of a Clinical Trial (ICH E6 Section 8) and as required by applicable regulations and/or guidelines. The investigator/institution should take measures to prevent accidental or premature destruction of these documents.

Essential documents (written and electronic) should be retained for a period of not less than fifteen (15) years from the completion of the Clinical Trial unless Sponsor provides written permission to dispose of them or, requires their retention for an additional period of time because of applicable laws, regulations and/or guidelines.

11.7 Confidentiality of study documents and patient records

The investigator must ensure anonymity of the patients; patients must not be identified by names in any documents submitted to Novartis. Signed informed consent forms and patient enrollment log must be kept strictly confidential to enable patient identification at the site.

11.8 Audits and inspections

Source data/documents must be available to inspections by Novartis or designee or Health Authorities.

11.9 Financial disclosures

Financial disclosures should be provided by study personnel who are directly involved in the treatment or evaluation of patients at the site - prior to study start.

[figure not shown]
12 Protocol adherence

Investigators ascertain they will apply due diligence to avoid protocol deviations. Under no circumstances should the investigator contact Novartis or its agents, if any, monitoring the study to request approval of a protocol deviation, as no authorized deviations are permitted. If the investigator feels a protocol deviation would improve the conduct of the study this must be considered a protocol amendment, and unless such an amendment is agreed upon by Novartis and approved by the IRB/IEC/REB it cannot be implemented. All significant protocol deviations will be recorded and reported in the CSR.

14.2 Appendix 2: Drugs that are prohibited or to be used with caution

In general, the use of any concomitant medication deemed necessary for the care of the patient is permitted in this study, except as specifically prohibited below. Combination administration of study drugs could result in drug-drug interactions (DDI) that could potentially lead to reduced activity or enhanced toxicity of the concomitant medication and/or LTT462.

The following lists are based on the Oncology Clinical Pharmacology Drug-Drug Interaction memo (released in April 2015). The FDA's Guidance for Industry, [Drug Interaction Studies - Study Design, Data Analysis and Implications for Dosing and Labeling \(February 2012\)](#), is the basis of the OCP DDI List, and it was supplemented with the data from the Indiana University School of Medicine's "Clinically Relevant" Table and the University of Washington's Drug Interaction Database.

The list of medications in [Table 14-6](#) and [Table 14-7](#) is meant to provide guidance and it is not a comprehensive list. If the patient requires to take a medication that is not in the list, but there might be a risk of DDI, please contact Novartis.

If a drug appears in [Table 14-6](#) (prohibited) as well as in [Table 14-7](#) (drugs to be used with caution), the drug should be considered as prohibited.

[figure not shown]
Please contact the Novartis Medical monitor with any questions.

Table 14-6 Drugs prohibited while on study

Category	Drug Names
Proton pump Inhibitor	Omeprazole, lansoprazole, dexlansoprazole, esomeprazole, pantoprazol, rabeprazole

Category

Drug Names

The table content is completely redacted with a large black box.

Table 14-7 Drugs to be used with caution while on study

Category	Drug Names
[Redacted Table Content]	

In the event that a drug appears in both the listings of prohibited and drugs to be used with caution, the drug is prohibited.

¹ LTT462 should be administered at least 1 hour before or 2 hours after an antacid

² LTT462 should be administered at least 3 hours before or 6 hours after an H2 receptor antagonist.

[Redacted Table Content]	
--------------------------	--

All changes to the planned analysis described in this document required before or after database lock will be made through an amendment or addendum, respectively. Note that obvious corrections will be made at the time of analysis to address minor formatting or spelling mistakes present in the TFL shells document without the need to amend.

The SAP, TFL shells and PDS documents may also serve as a reference for the creation of any outputs required outside of the CSR, e.g., MTD/RDE declaration, IB updates, abstracts, posters, presentations, manuscripts and management updates. Data used for these analyses will have a status aligned to the database lock guidance.

1.1 Study design

Novartis SAP	Confidential 13-May-2019 (11:03)	Page 5 CLTT462X2101

1.2 Study objectives and endpoints

Table 1-1 Primary and secondary objectives

Objective	Endpoint
Primary	
To characterize safety and tolerability of LTT462 and identify a recommended dose and regimen for future studies in adult patients with advanced solid tumors harboring MAPK pathway alterations.	Safety: Incidence and severity of adverse events (AEs) and serious AEs (SAEs), including changes in laboratory values, vital signs, and ECGs.
	Incidence and nature of DLTs (dose escalation only)
	Tolerability: Dose interruptions, reductions, and dose intensity
Secondary	
To evaluate the preliminary anti-tumor activity of LTT462	For both parts: Overall response rate (ORR), Disease Control Rate (DCR), Duration of Response (DOR), and Progression Free Survival (PFS) as per Response Evaluation Criteria in Solid Tumors (RECIST) version 1.1
To evaluate the pharmacokinetic (PK) profile of LTT462	Plasma concentrations and derived PK parameters of LTT462
To assess the pharmacodynamic (PD) effect of LTT462	Changes from baseline of the PD marker DUSP6 in tumor tissue and in blood.

2 Statistical Methods

2.1 Data analysis general information

Study data will be analyzed by Novartis personnel and/or designated CRO(s) using R

available in the programming environment

PK parameters will be calculated using non-compartmental methods available

Data from participating centers will be combined, so that an adequate number of patients will be available for analysis. No center effect will be assessed. The data will be summarized with respect to demographic and baseline characteristics, efficacy observations and measurements, safety observations and measurements, and all relevant pharmacokinetic (PK) and pharmacodynamics (PD) measurements using descriptive statistics (n, mean, standard

The primary clinical study report (CSR), if final DBL has not occurred, will include all patients' data reported during the dose escalation and dose expansion parts up to the time when all patients have potentially completed at least six cycles of treatment or discontinued the study. The primary CSR will include all outputs planned within the TFL shells document. A final (or closeout) CSR will be produced once all patients have discontinued the study.

Novartis	Confidential	Page 7
SAP	13-May-2019 (11:03)	CLTT462X2101

deviation, median, minimum, and maximum) for quantitative data and contingency tables (frequencies and percentages) for qualitative data.

Both pre and post intra-patient dose escalation data will be listed and summarized together under the one dose level/treatment group.

Cohorts of patients treated during the dose escalation part with the same dose levels, regimen will be pooled into one single *treatment group*.

Below an illustration of the grouping, there will be no difference between safety and efficacy layout of outputs (more details are included in the TFL shells document).

Table 2-1General display of information

		Dose Escalation		
	Treat	Treat	Treat	All
	A	B	C	patients
	N=xx	N=xx	N=xx	N=xx
	n (%)	n (%)	n (%)	n (%)
variable	xx	xx	xx	xx
	(xx.x)	(xx.x)	(xx.x)	(xx.x)
variable	xx	xx	xx	xx
	(xx.x)	(xx.x)	(xx.x)	(xx.x)
variable	xx	xx	xx	xx
	(xx.x)	(xx.x)	(xx.x)	(xx.x)

If during the course of the study different groups of interest are identified, the SAP will be updated accordingly.

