6.2.3.4 Intra-Patient dose escalation

Intra-patient dose escalation is not permitted at any time within the first 4 cycles of treatment. After the 4th cycle is completed, individual patients may be considered for treatment at a dose of LTT462 higher than the dose to which they were initially assigned. In order for a patient to be treated at a higher dose of LTT462, he or she must have tolerated the lower dose for at least 4 cycles of therapy (i.e. he or she must not have experienced any LTT462-related toxicity CTCAE grade ≥ 2 at the lower dose originally assigned). Moreover, the new, higher dose with which the patient is to be treated must be a dose that has completed evaluation and has not exceeded the MTD estimated by the Bayesian model given all available data.

There is no limit to the number of times a patient may have his or her dose of LTT462 increased. Further increase after the initial intra-patient dose escalation will be subject to the same rule as for the initial intra-patient dose escalation. Consultation and agreement with Novartis must occur prior to any intra-patient dose escalation occurring. These changes must be recorded on the Dosage Administration Record eCRF.

[figure not shown]
Data from the first cycle of treatment at the new dose level will not be formally included into the statistical model describing the relationship between dose and occurrence of DLT. However, this data will be incorporated into the clinical assessment of safety within a dose escalation teleconference.

With the exception of ophthalmological assessments (see [Section 7.2.2.7](#)), patients will continue with the visit schedule in line with the duration of their treatment (i.e. they would not have to restart at C1D1 assessments but continue from C5D1 if they).

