2.2 General definitions

Study drug and study treatment

Study drug and study treatment refer to LTT462 and are used interchangeable.

Date of first/last administration of study drug and study treatment

The date of first (last) administration of study treatment is derived as the first (last) date when a non-zero dose of study treatment LTT462 was administered and recorded on the Dosage Administration Record panel. For the sake of simplicity, the date of first (last) administration of study treatment will also be referred as start (last) date of study treatment.

Study day

The study day for all assessments/onset of events will be calculated using the start date of study treatment as reference. For assessments/events occurring on or after the start date of study treatment, study day will be calculated as:

Novartis	Confidential	Page 8
SAP	13-May-2019 (11:03)	CLTT462X2101

Study day (days) = Event date - Start date of study treatment + 1

Therefore, the first day of study treatment is study day 1.

For all assessment/onset of events occurring prior to the start of the study treatment, study day will be negative and will be calculated as:

Study day (days) = Event date – Start date of study treatment

On-treatment assessment/event

An on-treatment assessment/event is defined as any assessment/event in the time interval from the start date of LTT462 treatment until the last date of LTT462 treatment + 30 days inclusive.

LTT462 dose interruption

Study drug dose interruption is defined as a "total daily dose" equal to zero, between the first and last non-zero doses, following a non-zero total daily dose. This applies to any regimen, in our case QD and independently of the reason for interruptions.

LTT462 dose reduction

Time points at which the dose change flag is checked and the total daily dose is nonzero.

If the total daily dose at that time point is lower than the total daily dose at the time that the last non-zero dose was administered then the dose change is identified as a dose reduction.

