2.3 Analysis sets

Full Analysis Set (FAS)

The FAS will be the default to be used for all efficacy analyses. Listings of raw data will use the FAS, unless otherwise noted. It includes all patients who received at least one dose of study drug (full or partial). Patients will be classified according to the planned (i.e., assigned) treatment (dose level, regimen, _____).

Safety Set

The safety set will be the primary population for all safety related endpoints except determination of the dose-DLT relationship. It includes all patients who received at least one dose (full or partial) of study treatment. The statement that a patient did not experience an adverse event constitutes a valid safety assessment. Patients will be analyzed according to the treatment received, where treatment received is defined as:

- The treatment assigned, if it was received at least once, or
- The first study treatment received, if the treatment assigned was never received.

Dose-determining Set

The DDS consists of all patients from the safety set in the dose escalation part of the trial who either meet the following minimum exposure criterion and have sufficient safety evaluations

Novartis	Confidential	Page 9
SAP	13-May-2019 (11:03)	CLTT462X2101

during the first 28 days of dosing or discontinue earlier due to a DLT during the first 28 days of dosing. This constitutes an evaluable patient for the determination of MTD. Patients in the DDS will be identified prior to each dose escalation meeting and will be confirmed prior to database lock.

In this study, if data on AEs, vital signs, Labs, and dose administration is collected at least at study visits C1D1, C1D8 and C1D15, patient is considered as having sufficient safety evaluations. The statement that a patient did not experience an adverse event constitutes a valid safety assessment.

A patient is considered to have met the minimum exposure requirement if they have received at least 75% of the planned doses of each of the assigned combination drugs during the first cycle (the first 28 days of dosing). For all regimens proposed this equates to at least 21 of the planned 28 doses LTT462.

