2.9.2 Statistical model and method of analysis

DLTs (in the dose escalation part) will be analyzed using a BHLRM. The incidence of DLTs will be summarized by system organ class (SOC) and preferred term. The DDS will be used to analyze DLTs.

Statistical analysis of endpoints other than incidence of DLTs will be descriptive, based on the safety analysis set, no hypotheses or models will be considered. Details of analysis are provided in the safety and tolerability sections, respectively. Descriptive statistics will be provided on:

[figure not shown]
- The incidence by patients of AEs, independent of relationship to study drug, and also considering severity
- The incidence by patient of serious AE, independent of relationship to study drug
- Changes from baseline to worst post-baseline hematology and chemistry laboratory values
- Changes from baseline to worst post-baseline values of ECG parameters
- Changes in vital signs from baseline to worst post-baseline values
- Summary of dose intensity, and number and percentage of dose interruptions and reductions

Novartis	Confidential	Page 13
SAP	13-May-2019 (11:03)	CLTT462X2101

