2.11.1 Adverse events

Data handling

AEs will be coded and graded using the latest version of MedDRA and CTCAE, respectively, available at the time of reporting. If CTCAE grading does not exist for an AE, grades 1, 2, 3, or 4 corresponding to the severity of mild, moderate, severe, and life-threatening, respectively, will be used. CTCAE grade 5 (death) will not be used in this study. Death information will be collected during treatment, safety follow up, and post-treatment follow up.

Progression of malignancy (including fatal outcomes), if documented by use of appropriate method (for example, as per RECIST criteria for solid tumors, should not be reported as a serious adverse event.

Adverse events separate from the progression of malignancy (example, deep vein thrombosis at the time of progression or hemoptysis concurrent with finding of disease progression) will be reported as per usual guidelines used for such events with proper attribution regarding relatedness to the drug.

A patient with multiple CTCAE grades for an AE will be summarized under the maximum grade recorded for the event. A subject with multiple occurrences of an AE is counted only once in the AE category (e.g. SOC, preferred term).

The incidence of a given AE is defined as the ratio of total number of patients experiencing the given AE at least once (defined by its preferred term [PT]) divided by the total number of patients at risk (i.e. part of the safety set). The incidence of AEs will be performed on treatment-emergent events only, i.e., AE that first occurs or worsens during treatment up to 30 days following the last treatment administration. The listing of adverse events will include all events reported during the study conduct.

Reports

The following AE summaries will be produced, including maximum CTC grade 3/4, in addition to the primary analyses:

- AEs regardless of study drug relationship
- AEs suspected to be study drug related
- AEs leading to discontinuation of study drug, regardless of study drug relationship
- AEs which are not SAEs regardless of study drug relationship
- All SAEs regardless of study drug relationship
- On-treatment deaths with cause of death by preferred term
- All deaths, with cause of death by primary system organ class and preferred term

A missing AE start date will be imputed using the following logic matrix described below.

Novartis	Confidential	Page 17
SAP	13-May-2019 (11:03)	CLTT462X2101

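### After an intra-patient dose increase, adverse events and dose intensity stay in the lower assigned-dose column, and the visible SAP text plans no summary cut at the increase

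*SAP*

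**What the plan says.** Protocol 6.2.3.4 permits a patient to move to a higher dose once the fourth cycle is complete, with no limit on the number of increases. The condition is that "he or she must not have experienced any LTT462-related toxicity CTCAE grade" 2 or higher at the dose originally assigned. First-cycle data at the new dose are kept out of the DLT model. The protocol adds: "However, this data will be incorporated into the clinical assessment of safety within a dose escalation teleconference".

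For reporting, SAP 2.1 states: "Both pre and post intra-patient dose escalation data will be listed and summarized together under the one dose level/treatment group". That sentence does not say which dose level is meant. SAP 2.3 (and Protocol 10.1.2) settles it for the Safety Set, where the treatment received is defined as "The treatment assigned, if it was received at least once, or" otherwise the first treatment received. A patient who later escalates has already taken the assigned dose, so the column is the assigned dose.

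SAP 2.2 defines on-treatment events as those "from the start date of LTT462 treatment until the last date of LTT462 treatment + 30 days inclusive". SAP 2.11.1 says: "A patient with multiple CTCAE grades for an AE will be summarized under the maximum grade recorded for the event". Its Reports list opens: "The following AE summaries will be produced, including maximum CTC grade 3/4, in addition to the primary analyses"; one item on that list is adverse events suspected to be drug related. The primary displays in SAP 2.9.2 include "The incidence by patients of AEs, independent of relationship to study drug, and also considering severity". SAP 2.8.1 calculates dose intensity over the whole treatment period. SAP 2.4 identifies no subgroup analyses.

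**The concern.** Safety and tolerability are the primary endpoints, and they are tabulated by dose group. A column labelled with one dose will hold events and exposure from a higher dose for any escalated patient. The eligibility rule for an increase makes this one-sided for drug-related events: only patients free of related grade 2 or higher toxicity at the assigned dose may escalate, so whatever related toxicity of that grade they show comes later. The pooled column can therefore overstate toxicity at the assigned dose, and the contrast between neighbouring doses can shift in either direction. Some late events may be delayed effects of the assigned dose, but the pooled table cannot show which.

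These tables go into the clinical study report. SAP section 1 adds that the SAP may also serve as a reference for other outputs, naming the declaration of the maximum tolerated or recommended dose. A reader of the tables could separate the post-increase events only by working through the listings.

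**Working it through.** **Which events move.**

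- *Drug-related summary with maximum grade 3/4 (SAP 2.11.1).* The condition in Protocol 6.2.3.4 excludes related grade 2 or higher toxicity before the increase. Every grade 3/4 entry from a patient escalated according to the protocol is then a post-increase event shown in the lower-dose column, unless relatedness was reassessed later.
- *Primary displays regardless of relationship (SAP 2.9.2).* A preferred term first seen after the increase adds one patient to the lower-dose column. Worsening from grade 1 to grade 2 changes only the displays by grade.
- *Not affected.* The DLT model, the overdose-control decisions and the first-cycle DLT outputs.

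**Is there a cut anywhere?** The on-treatment window (SAP 2.2, 2.11), the incidence rule (SAP 2.11.1) and the dose-intensity formula (SAP 2.8.1) all run over the whole treatment period. No visible text describes a summary that stops at the increase or that groups events by dose at onset.

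The plan gives no figure on this point to reproduce. The following are illustrations with assumed patients.

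**Effect of one event on a column rate.** Protocol 6.2.3.2 requires at least 6 patients at a recommended dose: 1/6 = 16.7 points. In an assumed group of 12: 1/12 = 8.3 points.

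**Direction between doses.** Assume groups of 6 with 0, 1 and 2 events at 200, 300 and 400 mg (doses from Protocol Table 6-2), and add one post-increase event to the 300 mg column.

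| Contrast | Before | After |
|---|---|---|
| 300 minus 200 mg | 1/6 − 0 = 17 points | 2/6 − 0 = 33 points |
| 400 minus 300 mg | 2/6 − 1/6 = 17 points | 2/6 − 2/6 = 0 points |

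**Share of on-treatment time after the increase.** Assume the increase falls on day 1 of cycle 5, so 4 × 28 = 112 days come before it.

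- Stop after 6 cycles: window 168 + 30 = 198 days; 198 − 112 = 86; 86/198 = 43%.
- Stop after 8 cycles: window 224 + 30 = 254 days; 254 − 112 = 142; 142/254 = 56%.

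**Dose intensity.** Assume once-daily dosing with no missed doses, 100 mg for four cycles and then 200 mg. The day 2 dose of cycle 1 is omitted (Protocol 6.1.1), so cycles 1 to 4 hold 4 × 28 − 1 = 111 doses. The formula is cumulative dose divided by scheduled doses (SAP 2.8.1).

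- 6 cycles: (111 × 100 + 56 × 200)/167 = 22,300/167 = 133.5 mg.
- 8 cycles: (111 × 100 + 112 × 200)/223 = 33,500/223 = 150.2 mg.
- Mean of a 100 mg group of 6 with one such patient and five at 100 mg: (500 + 133.5)/6 = 105.6 mg at 6 cycles; (500 + 150.2)/6 = 108.4 mg at 8 cycles.

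**The case against.** The strongest reply is that this is an openly declared convention, consistent with the Safety Set and Full Analysis Set definitions and contradicted nowhere. That is true, and it is why the assigned-dose tables should remain the main display. It does not make the by-dose reading of late events any clearer.

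Other points on that side:

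- *Routes for extra analyses exist.* Protocol 10.4.4 allows supportive safety analyses to be defined before database lock, and SAP 2.1 allows an update if groups of interest emerge. Both are generic and commit to no such table, although either could carry the fix.
- *The table shells and dataset specifications were not available, and some SAP text is blacked out.* A cut could be specified there. This stands, and the conclusion is limited to the visible text.
- *Dose selection is largely insulated.* This also stands: the model uses first-cycle data, and first-cycle data at the new dose reach the teleconference. SAP section 1 says only that the SAP may serve as a reference for the dose declaration; it does not say that the pooled tables drive it.
- *The listings allow tracing, and at least 21 patients are expected, so cross-checking may be modest work.* Fair, but it leaves the task to each reader.
- *A cut at the increase is itself imperfect.* It drops any later time back at a lower dose, shortens follow-up for the patients who tolerated treatment best, and loses delayed effects of the assigned dose. This stands, and it is the reason to add the cut tables rather than substitute them.

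**Conclusion.** The concern holds. Taken together, SAP 2.1 and 2.3 place all post-increase adverse events, serious adverse events and exposure in the lower, originally assigned column, and no visible text provides a summary cut at the increase. For drug-related grade 3/4 events in escalated patients the attribution is systematic, because of the condition for escalating. This assumes that the condition was followed and that relatedness was not later revised.

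The size depends on how many patients escalate, which the documents do not give; with none, the effect is nil. With one event from one patient it is 17 points in a group of 6 and 8 points in a group of 12. The group-level effect on dose intensity is small. The issue concerns the interpretation of the by-dose safety tables, not the dose-escalation decisions. It is worth correcting because the tables carry the primary endpoints and the correction is cheap.

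**What to change.** Keep the tables by assigned dose as the main display. Add to the SAP that, if any patient has an intra-patient increase:

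1. supplementary adverse event, serious adverse event and dose-intensity summaries will be produced by assigned dose, using data only up to the day before the first increase; and
2. post-increase events will be flagged in the adverse event listing with the dose at onset, or at worsening for events that began earlier.

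The cost is one derived date from the Dosage Administration Record, a few repeat tables, a listing flag and one or two sentences of SAP text. None of the outputs is needed if no patient is escalated. The supplementary tables give up follow-up (43% of the on-treatment window for the escalated patient in the 6-cycle illustration) and may leave out late effects of the assigned dose. The SAP should therefore say that they are to be read beside the pooled tables.
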